#### **8.4.2 Interim analyses**

Two interim analyses will be planned, a first when 40% of the sample size (38 patients) is reached and a second when 60% of the sample size (57 patients) is reached. During these interim analyses the significance will be tested. If significance is found, the trial can be terminated with the patients already collected.

38 patients guarantee a statistical power of 80% if at least 93.9% of these are free of 'event' (intended as procedure incomplete or serious adverse event). 57 patients guarantee a statistical power of 80% if at least 91.8% of these are free of 'event'.

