## 3. STUDY ENDPOINTS

### 3.1 Primary Endpoints:

Efficacy:

The primary efficacy endpoint is the percentage minor or equal to 10% of incomplete long-lasting colonoscopies (colonoscopy is defined completed when caecal intubation is achieved)

AND

Safety:

Medical adverse events and medical device adverse events will be collected during the study.

The primary safety endpoints are:

The absence of device-related serious adverse events.

AND

The evaluation of the equality or reduction of the adverse events rates compared to diagnostic colonoscopies without Endorail.

The adverse events assessed are:

- Occurrence of general adverse events and medical device incidents;
- Occurrence of specific adverse events: gastrointestinal bleedings, intestinal perforation, mucosal petechiae and abdominal pain.

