### 8.2 Determination of Sample Size

Efficacy (first primary objective) will be assessed by measuring the colonoscopy completion rate in long-lasting procedures, which is a measurable parameter of clinical value recognized by international medical societies. Safety (second primary objective) will be assessed by measuring the rare of adverse events. They are classified into: serious gastrointestinal events; myocardial infarction; stroke; pneumonia. Based on the literature [30]; their occurrence rates in screening or surveillance colonoscopy are 47 persons, 4 persons, 7 persons and 10 persons per 100'000, respectively.

These two objectives are merged in one indicator, which is equal to 1 for each subject if the procedure is incomplete or an adverse event occurs, and 0 otherwise.

The non-completion rate of long-lasting colonoscopies conducted with Endorail is expected to be around 10%. This will be compared to the above-mentioned threshold of 20% for incomplete procedures. It should be noted that this threshold is conservative and represents the most critical setting for comparison with respect to the state of the art, as it is derived from the lower bound of the range from the literature.

When including the safety to provide the expected value of the indicator for Endorail and the corresponding threshold, the above values of 10% minimally change, as the adverse event

occurrence rate is 0.068% (given by the sum of the occurrence of the 4 events reported above per 100'000 persons, expressed in percentage).

With a significance level  $\alpha$  of 5%, assuming a proportion of outcome of 10.1%, 85 patients allow to test with a power of 80% the  $H_0: p \geq 20\%$  vs  $H_1: p < 20\%$ , where 20% is the estimated percentage of incomplete procedure from literature.

The chosen number is then increased by the 10% to account for possible drop-out (e.g., cases to be discarded, losses to follow-up, etc.), resulting in  $85/0.90 = 95$  patients to be actually enrolled.

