### **8.4 Planned Analyses**

The statistical analysis plan will be finalized before Data Base Lock and it will include a more technical and detailed description of the statistical analyses described in this section. This section is a summary of the planned statistical analyses.

All data obtained in this study and documented in the eCRFs will be listed and summarized as appropriate:

- for quantitative variables: standard quantitative statistics (N, mean, standard deviation, median, interquartile range, minimum and maximum);
- for qualitative variables: frequency distribution [number of non-missing observations (N) and percentages (%)].

A statistical test will be performed to assess the significant difference of the indicator with respect to the threshold and statistically prove efficacy of Endorail in long-lasting procedures. Due to the type of variable, the exact binomial test will be adopted. Additionally, considering as alternative hypothesis that the rate observed in the analyzed population is less than the respective threshold, the one-tailed test will be adopted.

Medical adverse events and medical device adverse events will be collected during the study.

The number of adverse events (AEs) – related or not to the medical device – and the number and proportion of patients with at least one AE will be presented.

All adverse events will be tabulated by System Organ Class (SOC) and Preferred Term (PT) after medical coding using the Medical Dictionary for Regulatory Activities (MedDRA) thesaurus version 24.1. The primary SOC and the PT will be used for the analysis of the frequency

distribution.

The frequency of occurrence of specific adverse events (gastrointestinal bleedings, intestinal perforation, mucosal petechiae, abdominal pain) will be presented by means of default descriptive statistics.

Statistical analyses will be carried out using R Statistical Software (Foundation for Statistical Computing, Vienna, Austria).

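### The 10% efficacy endpoint rests on a point estimate, the trial may stop early when that estimate is low, and no interval or estimate allowing for the stopping is planned

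*Combined protocol and SAP*

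**What the plan says.** Section 3.1 defines efficacy as an observed rate: "The primary efficacy endpoint is the percentage minor or equal to 10% of incomplete long-lasting colonoscopies". The primary objective (2.1) uses the same 10% figure, and sections 1.2.6 and 1.5 state the aim as a rate below the guideline threshold of 10%.

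The formal hypothesis is different. Sections 8.1 and 8.2 set the null value at 20%, and section 8.4 says: "A statistical test will be performed to assess the significant difference of the indicator with respect to the threshold". For that test, "the exact binomial test will be adopted" and "the one-tailed test will be adopted". No test or confidence bound is attached to 10%.

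Sections 4.6, 8.3 and 8.4.2 provide two looks, at 38 and 57 patients, and say: "If significance is found, the trial can be terminated with the patients already collected". No adjusted limit is given. The planned summary of a binary variable in 8.4 is the number of observations and the percentage. A separate SAP with more technical detail is to be completed before the database is locked. Section 8.4 describes itself as a summary.

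**The concern.** Stopping for significance selects trials whose rate so far happens to be low. The raw proportion from a trial stopped this way is biased downwards, and here it is the quantity set against 10%. A significant first look needs at most 3 events in 38, which is 7.9%, so it meets the 10% criterion automatically. Without an interval, a reader shown only 7.9% cannot see that the one-sided 95% upper limit is 19.2%.

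At stake is the evidence for the stated endpoint. The test against 20% does not support a claim about 10%, so that claim depends on which estimate is reported and on what is shown beside it.

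**Working it through.** **Inputs.** Section 8.2: null value 20%, planning rate 10.1%, one-sided 5%, 80% power, 85 evaluable and 95 enrolled. Section 8.4: one-sided exact binomial test. Section 8.4.2: looks at 38 and 57, with 80% power stated for event-free rates of 93.9% and 91.8%, that is, event rates of 6.1% and 8.2%.

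**Reproducing the plan's figures.** The normal approximation gives n = [1.645·√(0.20·0.80) + 0.842·√(0.101·0.899)]² / (0.20 − 0.101)² = (0.658 + 0.254)² / 0.0098 = 84.8, so 85. Then 85/0.90 = 94.4, so 95.

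At an unadjusted one-sided 5%, the exact test is significant at:
- 3 or fewer of 38 (p = 0.039)
- 6 or fewer of 57 (p = 0.045)
- 10 or fewer of 85 (p = 0.033), or 12 or fewer of 95 (p = 0.042)

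With these limits the power is 80.0% at 6.1% with 38 patients and 81.6% at 8.2% with 57. This fits section 8.4.2 and indicates that the looks are at the unadjusted 5%.

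**Bias of the raw rate.** All stopping paths were enumerated exactly, with every significant look stopping the trial. At a true 10.1% and final n = 85:

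| Stops at | Probability | Mean raw rate |
|---|---|---|
| 38 | 45.7% | 5.8% |
| 57 | 22.2% | 9.5% |
| 85 | 32.1% | 13.1% |

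Overall mean: 0.457·5.84 + 0.222·9.47 + 0.321·13.10 = 9.0%. With final n = 95 it is 8.9%. Given an early stop (probability 67.9%) the mean is (0.457·5.84 + 0.222·9.47)/0.679 = 7.0%.

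**Chance of observing 10% or less.** The results that qualify are 0–3 of 38, 4–5 of 57, and at the end up to 8 of 85 or 9 of 95. At a true 15% with final n = 85 the sum is 0.158 + 0.038 + 0.009 = 0.204 (rounded from 0.2041).

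| True rate | With looks (n = 85 / 95) | Fixed sample (n = 85 / 95) |
|---|---|---|
| 10.1% | 59.2% / 60.1% | 50.7% / 50.5% |
| 12% | 41.6% / 42.1% | 29.5% / 28.3% |
| 15% | 20.4% / 20.5% | 9.3% / 8.1% |
| 20% | 4.6% / 4.6% | 0.7% / 0.5% |

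**What adjustment would show.** Whitehead ranges cover final n of 85 and 95. The median-unbiased column uses stage-wise ordering with mid-p. The last two columns are one-sided 95% upper limits.

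| Result | Raw | Whitehead bias-adjusted | Median-unbiased | Upper limit, naive | Upper limit, stage-wise |
|---|---|---|---|---|---|
| 3/38 | 7.9% | 8.9–9.0% | 8.2% | 19.2% | 19.2% |
| 5/57 | 8.8% | 9.9–10.0% | 10.4% | 17.6% | 19.7% |
| 6/57 | 10.5% | 11.7–11.8% | 11.4% | 19.7% | 20.7% |

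Without the mid-p correction, the median-unbiased estimate for 5/57 is 10.8%. At the final look the stage-wise median-unbiased estimate cannot fall below about 12%: 8/85, raw 9.4%, becomes 12.2%.

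**The case against.** The strongest points on the other side are these.

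- *The plan does not say that the raw rate will be reported after an early stop.* This stands. A reader might infer a commitment to the raw rate, but the documents only leave the estimate unspecified and defer detail to a later SAP. That SAP need only be final by database lock, which can fall after both looks.
- *An early stop need not give a favourable result.* This stands. A reader might infer that stopping guarantees the endpoint, but 6/57 is significant and, at 10.5%, misses 10%.
- *Part of the size comes from the unadjusted limits.* This stands. Under assumed O'Brien-Fleming-type limits of 0/38 and 4/57, the chance of stopping at 38 at a true 10.1% falls from 46% to 2%, and the overall mean is 9.5–9.6%. The chance of observing 10% or less becomes 32% at a true 12% and 11% at a true 15%. Bias is reduced, not removed.
- *Stopping is optional, and the looks test a composite.* Both stand. The figures are the full effect if every significant look stops the trial. Section 8.2 counts any adverse event, while 8.1 and 8.4.2 count serious ones. Section 8.2 expects events to add only 0.068%. If non-serious events count, the figures do not carry over to incompletion.
- *Judging 10% on the stage-wise median-unbiased estimate would be a poor remedy.* This stands. It barely moves a first-look stop (3/38: 7.9% to 8.2%), yet every trial that reached the final look would fail automatically. At a true 10.1% that is a 32% chance.
- *The inferential decision is against 20%.* True, but 10% is the stated primary endpoint, and this gap is why its estimate needs care.

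**Conclusion.** The point holds as a gap in the plan that should be closed, of moderate weight. The plan sets a point estimate against 10%, permits stopping when that estimate is low, and specifies no interval or estimate suited to the design.

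Overall bias at the planning rate is modest, about 1 percentage point. It is about 3 points given an early stop, which has a 68% chance there. The effect on the 10% statement is larger when the true rate misses the target: at a true 15%, the chance of an apparent pass roughly doubles.

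These sizes assume that every significant look stops the trial, that the limits are the unadjusted 3/38 and 6/57, and that the composite approximates incompletion. The true rates of 12%, 15% and 20% are chosen for illustration; only 10.1% is the plan's own expected rate.

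**What to change.** In sections 8.4 and 8.4.2, before the first look:

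1. State that the raw incompletion rate will be reported with an exact confidence interval that respects the stopping rule, for example by stage-wise ordering.
2. Name one bias-adjusted estimate to stand beside it. A Whitehead-type estimate is one candidate, and it also moves a first-look result.
3. State that after an early stop the 10% statement is presented with that interval and adjusted estimate, and not on the raw rate alone.
4. Do not make the stage-wise median-unbiased estimate the sole 10% criterion.

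The cost is SAP wording, a small extra analysis and a less favourable reported figure. After 5/57, for example, a raw 8.8% would stand beside 10.4–10.8% if the median-unbiased estimate is the one named, with an upper limit of 19.7% where the naive limit is 17.6%. No patients or procedures are added.

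One consequence should be foreseen. With unadjusted looks the total type I error is 7.6% (final n = 85) or 8.4% (final n = 95), so the interval can include 20% although the naive test is significant: 6/57 has a stage-wise upper limit of 20.7%. Setting adjusted interim limits at the same time would keep test and interval consistent and reduce the bias.

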#### **8.5 Handling of missing data and drop-outs**

Not applicable. Missing data will not be replaced.

## 9. QUALITY ASSURANCE AND CONTROL

All participant data relating to the study will be recorded on eCRF. The investigator is responsible for verifying that data entries are accurate and correct by electronically signing the eCRF.

The investigator must maintain accurate documentation (source data) that supports the information entered in the eCRF.

The investigator must permit study-related monitoring, audits, IRB/IEC review, and regulatory agency inspections and provide direct access to source data documents. Monitoring details describing strategy (eg, risk-based initiatives in operations and quality such as Risk Management and Mitigation Strategies and Analytical Risk-Based Monitoring), methods, responsibilities, and requirements, including handling of noncompliance issues and monitoring techniques (central, remote, or on-site monitoring) are provided in the monitoring plan. The sponsor or its designee is responsible for the data management of this study including quality checking of the data.

The sponsor assumes accountability for actions delegated to other individuals (e.g. Contract Research Organizations).

Study monitors will perform ongoing source data verification to confirm that data entered into the eCRF by authorized site personnel are accurate, complete, and verifiable from source documents, that the safety and rights of participants are being protected, and that the study is being conducted in accordance with the currently approved protocol and any other study agreements, ICH GCP, and all applicable regulatory requirements.

### 9.1 Data handling and record keeping / archiving

Records and documents, including signed ICFs, pertaining to the conduct of this study must be retained by the investigator for 25 years after study completion unless local regulations or institutional policies require a longer retention period. No records may be destroyed during the retention period without the written approval of the sponsor. No records may be transferred to another location or party without written notification to the sponsor.

#### 9.1.1 Case Report Forms

The study will be conducted in compliance with the dictates of the Helsinki declaration and in accordance with the rules of good clinical practice (Ministerial Decree of 15/07/1997 and subsequent amendments) as well as with the applicable regulatory provisions. Each participating center will maintain the medical records and research data of this study in an appropriate manner, in accordance with section 4.9 of the ICH-GCP E6, with the provisions of the regulatory bodies and the institution to which it belongs to ensure the protection of the confidentiality of the patients. As a participant in a clinical study, each center will allow staff authorized by the sponsor and regulatory agencies to review (and when permitted by law, to copy) medical records in order to check the quality of the data, for audits and for evaluations of the study safety and progress.

Source documents are all the information, original records of clinical findings, observations, or other activities of a clinical study necessary for the reconstruction and evaluation of the study itself. Examples of these original documents and records include, but are not limited to, medical records, clinical charts, laboratory notebooks, memos, patient diaries or evaluation lists, data recorded by automated tools, copies or transcripts certified after verification that these are accurate and complete, microfiche, photographic negatives, microfilm or magnetic media, plates obtained with

x-rays, subject cards and records kept in pharmacies, laboratories, and in the technical-medical departments involved in the clinical study.

Data collection is the responsibility of the staff at the center involved in the clinical study under the supervision of the center's Principal Investigator. The electronic data collection form (eCRF) is the main tool for collecting study data. The researcher should ensure the accuracy, completeness, legibility and timeliness of the data reported in the eCRF and in the same way as the other data reported.

The data reported in the eCRF, which derive from source documents, must be identical to the original ones and where this is not the case, the discrepancy must be explained. All data requested by the eCRF must be registered. Any missing data must be explained. Any changes or corrections to a paper CRF (in case the eCRF is not available for any reason) or document must be dated, listed next to the initials of the compiler, explained (if necessary) and must not obscure the original data. The investigator should keep track of the changes and corrections made to the eCRFs.

The institution should maintain the study documents as specified in the essential documents for conducting a clinical study (ICH-GCP E6, section 8) and as required by regulatory bodies and guidelines. The institution should take measures to prevent accidental or premature destruction of the documentation.

Essential documents (written and electronic) should be kept for a period of time not less than twenty-five (25) years from the completion of the study, unless the Promoter provides a written document that allows for the disposal and conservation of data for an additional period of time if permitted by law, regulatory bodies and/or guidelines.

The data will be inserted and managed through the use of the electronic CRF (eCRF) developed through the ICE platform and accessible via a specific URL address that will be provided at the moment of the SIV. To protect security and privacy, only authorized users will be allowed to access the eCRF through the use of individual access credentials (each user will be provided with unique username and password). The login credentials will be generated by the database administrator and communicated to the user via email. The user must change the password at the first access. The password will need to be changed every 3 months.

The data collected will be pseudo anonymized; for each participating subject an alpha numeric code (subject code) will be generated consisting of the center code, a spacer character and the subject number (e.g. CTR 01-01) and the data will be stored electronically. To keep track of the association between the medical record and the subject code, each center will compile a study specific form, as indicated in section 4.4. These forms, if in hardcopy must be kept in a place with limited access and locked, if in electronic form, must be kept in a separate, encrypted (AES-256 encryption) and password protected file; these forms will never be shared with the Promoter, with the database administrator and not even with the study statistician.

### 9.1.2 Specification of source documents

Source documents provide evidence for the existence of the participant and substantiate the integrity of the data collected. Source documents are filed at the investigator's site. Data entered in the eCRF that are transcribed from source documents must be consistent with the source documents, and any discrepancy must be explained. The investigator may need to request previous medical records or transfer records, depending on the study. Also, current medical records must be available.

The source documents for this study will be the patient's paper medical report, where are recorded

all the information needed to complete the eCRF. All the information inserted in the eCRF will be in accordance with the paper medical report. Among the data requested from the eCRF there are demographic data, visit dates, participation in study and Informed Consent Forms, SAEs, AEs, concomitant medication, medical history, and many other results of relevant examinations.

### **9.1.3 Record keeping / archiving**

All study data must be archived for a minimum of 25 years after study termination or premature termination of the clinical trial.

Records and documents, including signed ICFs, pertaining to the conduct of this study must be retained by the investigator for 25 years after study completion unless local regulations or institutional policies require a longer retention period.

## **9.2 Data management**

### **9.2.1 Data Management System**

The CRFs in this trial are implemented electronically using a dedicated EDC system (ICE, Integrated Clinical Trial Environment, Advice Pharma) that fulfils the legal requirements for clinical trials. The EDC system is activated for the user only after successfully passing a formal test procedure. All data entered in the EDC are stored on a Linux server in a dedicated Oracle database.

### **9.2.2 Data security, access and back-up**

The server hosting the EDC system and the database is kept in a locked server-room. Only the system administrators have direct access to the server. A role concept with personal passwords (site investigator, statistician, monitor, administrator etc.) regulates permission for each user to use the system and database as he/she requires.

All data entered into the EDC are transferred to the database using Secure Sockets Layer (SSL) encryption. Each data point has attributes attached to it identifying the user who entered it with the exact time and date to ensure proper audit-trail. Retrospective alterations of data in the database are recorded by time, table, data field and altered value. A multi-level back-up system is implemented.

### **9.2.3 Analysis and archiving**

At interim and final analyses, data files will be extracted from the database into statistical packages to be analysed. The status of the database at this time is recorded in special archive tables. The study database with all archive tables will be securely stored by Advice Pharma. The sponsor also keeps the Trial Master File and interim and final reports both in electronic and in hard copy for at least 25 years after trial completion. Site will archive the Investigator Site File and Source Data for at least 25 years after trial completion.

### **9.2.4 Electronic and central data validation**

Data is checked by the EDC system for completeness and plausibility. Furthermore, selected data points are cross-checked for plausibility with previously entered data for that participant. In addition, central data reviews will be performed on a regular basis to ensure completeness of the data collected and accuracy of the primary outcome data. Data validation process is performed in accordance with the local regulations, with the FDA CFR 21 PART 11, GMP V.4 Annex 11, Data integrity, GAMP5 guideline and Good Practices for Computerized Systems in regulated “GXP” environments. Pharmaceutical Inspection Convention/Pharmaceutical Inspections Co-operation Scheme (PIC/S).

